Organ failure events	Organ failure events from after surgery to Day 180 (applicable during any hospitalization)							

Abbreviations: AE = adverse event; N/A = not applicable; PDI = protocol-defined infection; SAE = serious adverse event.

a. If surgery occurs on Day 10 after vaccination, the e-diary need not be completed on the day of surgery.

UNSCHEDULED STUDY VISITS, CONTACTS, AND SURVEILLANCE PERIODS

Table 3 shows the list of unscheduled visits that are to occur when certain conditions are met. Refer to Table 4 for unscheduled visit procedures.

Table 3. Unscheduled Study Visits, Contacts, and Surveillance Periods

Visit ID	1	2			3	4	5	6
Protocol Activity	Enrollment and Day of Vaccination	Index Hospital Admission			Telephone Call 	Day 42 Postoperative Evaluation	Day 90 Postoperative Evaluation	Day 180 Postoperative Evaluation
		Day of Surgery	Day After Surgery	Day of Discharge				
Study Day	Day -60 to Day -10	Day 1	Day 2	(Day Variable)	Day 21	Day 42	Day 90	Day 180
Visit Window	Day -60 to Day -10	N/A	N/A	N/A	Day 18 to Day 26	Day 35 to Day 49	Day 83 to Day 97	Day 178 to Day 192
UNSCHEDULED VISITS AND CONTACTS								
Severe local reaction or fever telephone contact  (Section 6.4.1.1.1)	May occur within 10 days after vaccination							
Severe systemic event telephone contact  (Section 6.4.1.1.2)	May occur within 10 days after vaccination							
Severe local reaction or fever assessment visit (Section 6.4.1.2)	May occur within 10 days after vaccination							
BSI/SSI assessment visit (Section 6.4.2)		
 • May occur postoperatively during the index hospital admission • May occur after discharge from the index hospital 						
Hospitalization visit (Section 6.4.3)		May occur at any time after discharge from the index hospital						

Abbreviations: BSI = bloodstream infection; N/A = not applicable; SSI = surgical-site infection.

STUDY PROCEDURES ASSOCIATED WITH UNSCHEDULED STUDY VISITS

The Study Procedures Associated With Unscheduled Study Visits table provides an overview of the unscheduled visit requirements. Refer to the Study Procedures ([Section 6.4](#)) and Assessments ([Section 7](#)) sections of the protocol for detailed information on each procedure and assessment required for compliance with the protocol.

Table 4. Study Procedures Associated With Unscheduled Study Visits

Protocol Procedure	Severe Local Reaction or Fever Telephone Contact	Severe Systemic Event Telephone Contact	Severe Local Reaction or Fever Assessment Visit	BSI/SSI Assessment Visit	Hospitalization Visit
Determine whether a severe local reaction or fever assessment visit is required	X				
Determine whether the severe systemic event meets Grade 4 and/or SAE criteria		X			
Measure temperature (°C or °F)			X		
Measure redness and swelling			X		
Grade pain			X		
Assess lymphadenopathy			X		
Collect colonization swab samples from the nose and throat				X	
Collect blood culture samples				X	
For an SSI that is operatively incised and/or spontaneously draining, collect a wound culture swab				X	
Collect a blood sample for immunogenicity				24 mL	24 mL ^a
Record antibiotic therapy				X	X
Adverse event collection as appropriate				X	X
Collect healthcare utilization data					X
If a PDI event is suspected, complete PDI event requirements ^b				X	X
If a BSI and/or SSI is identified or suspected, complete all procedures for a BSI/SSI assessment visit ^c					X
Assess for organ failure ^d					X
Perioperative data collection for index surgery reoperation and revision					X

Abbreviations: BSI = bloodstream infection; PDI = protocol-defined infection; SAE = serious adverse event; SSI = surgical-site infection.

- Collect only if subject has multiple-organ failure.
- Refer to [Section 7.1.1](#) for PDI events.
- Refer to [Section 6.4.2](#) for the BSI/SSI assessment visit.
- Refer to [Section 7.2.3](#) for assessment of organ failure.

TABLE OF CONTENTS

ABBREVIATIONS	9
PROTOCOL SUMMARY	12
INTRODUCTION	12
LIST OF TABLES	30
LIST OF FIGURES	31
APPENDICES	31
1. INTRODUCTION	32
1.1. Mechanism of Action/Indication.....	32
1.2. Background and Rationale	32
1.2.1. Healthcare-Associated S aureus Disease.....	32
1.2.1.1. Postoperative S aureus Disease.....	33
1.2.2. Rationale for Evaluation of SA4Ag Efficacy in the Prevention of Postoperative S aureus Disease in Patients Undergoing Elective Surgery.....	34
1.2.3. Vaccine Antigen Composition.....	35
1.2.4. Clinical Experience.....	35
1.2.4.1. First-in-Human Trial of SA3Ag (Phase 1, Study B2251002)	35
1.2.4.2. First-in-Human Trial of SA4Ag (Phase 1/2a, Study B3451001)	36
1.2.4.3. Trial of SA4Ag in Elderly Subjects (Phase 1/2a, Study B3451011)	36
1.2.4.4. Duration-of-Immunogenicity Study (Phase 2, Study B3451014)	36
1.2.5. Summary of Benefit-Risk Assessment	37

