2.5. Endpoint Adjudication

To maintain the scientific integrity, this protocol will use an independent EAC for adjudication of all primary and secondary efficacy endpoints, exploratory endpoints of ISA disease ([Section 7.1.1.2](#)), multiple-organ failure (MOF), and death, as summarized below. The EAC's assessment of these events will represent the final confirmed classification of the event.

The primary and/or secondary efficacy-related events for adjudication include all reported BSI and SSI events. The EAC is responsible for adjudicating whether BSI and SSI events fulfill the protocol-defined clinical criteria, and whether the confirmed infections are attributable to microbiologically confirmed *S aureus*, attributable to other pathogen(s), or without microbiological confirmation.

Furthermore, the EAC is responsible for adjudicating all other reported PDI events. As with BSI and SSI events, the EAC will confirm whether these events fulfill the protocol-defined clinical criteria, and whether these events represent microbiologically confirmed *S aureus* infection.

In addition, any other invasive infection (irrespective of the causative pathogen) will be adjudicated by the EAC.

The most adverse outcomes of postoperative infections are MOF and death. Therefore, in addition to the PDI adjudication responsibilities mentioned above, the EAC is also responsible for adjudicating whether reported organ failure (OF) events meet the protocol-defined clinical criteria for OF/MOF, and whether the confirmed OF/MOF events and all reported deaths are attributable to microbiologically confirmed *S aureus*, attributable to other pathogen(s), or without microbiological confirmation ([Section 7.2.3](#)).

The detailed event adjudication criteria, documentation requirements, responsibilities, EAC membership requirements, and training are found in the event adjudication committee charter (EACC). The EAC will remain blinded to subject vaccine assignments. To facilitate EAC adjudication, in addition to the data captured in the case report form (CRF), documents that support the clinical and microbiological criteria specified in Appendix 1 will be provided by investigators in conjunction with the sponsor's study team.

Any SAE that is adjudicated by the EAC and determined NOT to meet endpoint criteria is reported back to the investigative site of incidence; the investigator at the study site must

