6.4.2. BSI/SSI Assessment Visit

At any time after surgery until completion of study participation, when a subject is suspected of having a BSI and/or SSI, a BSI/SSI assessment visit will be conducted.

If the BSI/SSI assessment visit occurs during the index study admission, or is coincident with the Day 21 telephone contact or the Day 42, Day 90, or Day 180 postoperative assessment visit, the BSI/SSI assessment visit study procedures common to both visits may be combined.

The following procedures will be conducted:

- Complete a PDI event report for BSI and /or SSI, as appropriate for the PDI(s), as described in [Section 7.1.1](#).
- Collect and process a blood sample of approximately 24 mL for immunogenicity assessments.
- Collect colonization swab samples from the nose and throat.

- Collect blood culture sample(s) for any suspected BSI or deep incisional or organ/space SSI and, when clinically indicated, for a superficial SSI.
- For an SSI that is operatively incised and/or spontaneously draining, collect a wound culture swab as per local clinical laboratory guidance. Where possible, tissue and fluid samples are to be taken prior to commencing administration of antibiotics.
- Record antibiotic therapy as concomitant medication(s) as described in [Section 5.4](#).
- Determine whether any AEs or SAEs have occurred or require updating since the last subject assessment. Record and report AEs as described in [Section 8](#) and according to the Schedule of Activities for Adverse and Study Event Reporting (Table 2).
- Complete the source documents and CRF.

In the event that a subject is identified as having a suspected BSI and/or SSI and it is not possible to complete the BSI/SSI assessment visit (eg, in the event that the investigator is made aware of an infection that has already been treated to resolution by medical personnel external to the study team, and where there are no active signs or symptoms of infection), a PDI event report will be completed regardless.

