7.1. Efficacy Assessments

7.1.1. PDI Events

All subjects who undergo the index surgical procedure will be monitored for PDIs after surgery until the Day 180 postoperative evaluation.

[figure not shown]
The investigator will review all suspected PDIs against the clinical criteria provided in Appendix 1. Where the clinical criteria are met, the following procedures will be conducted:

- Notify the sponsor that a PDI event has occurred.
- Complete the requirements for a BSI/SSI event ([Section 6.4.2](#)) or an ISA event ([Section 7.1.1.2](#)).
- Report the PDI event in the CRF.

If an infection occurs after discharge from the index hospital, and the infection is managed or treated by a noninvestigator physician or at a nonstudy hospital, the study investigator will contact the treating noninvestigator physician/hospital to obtain the information required (eg, medical or hospital records, clinical, diagnostic, and microbiological data) to determine whether the infection meets PDI clinical criteria. If the clinical criteria are met, the investigator will complete the PDI event report noted above and notify the sponsor.

For the purposes of this study, PDIs will include all the infections listed in Table 6 and Table 7. As shown in Figure 1, the relationships between ISA, BSI, and SSI overlap, insofar as all BSI and SSI, with the exception of superficial SSI, are considered to be ISA disease.

Figure 1. Protocol-Defined Infections (Venn Diagram)

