8.6.1. Protocol-Specified Serious Adverse Events

Unless the investigator believes that there is a causal relationship between investigational product and the efficacy endpoints specified below, the events noted below should not be reported by the investigator as SAEs as described in [Section 8.14.1](#).

The following events are anticipated to occur in a study population following spinal surgery:

- Suspected or confirmed BSI and/or deep incisional or organ/space SSI
- Suspected or confirmed superficial SSI

[figure not shown]
Any suspected BSI or SSI event has the potential to meet endpoint criteria and is therefore to be adjudicated by the EAC. Reporting requirements (Figure 2) are summarized below while additional details are provided in the SRM:

- If the EAC confirms that the event meets the primary or secondary endpoint criteria, the event is **not reported as an SAE**.
- If the EAC confirms that the event **does not meet** the primary or secondary endpoint criteria, the event is reported back to the investigator as a nonendpoint SAE. The investigator will evaluate and **report the event as an SAE** (and AE), in accordance with the time frames described in the Serious Adverse Event Reporting Requirements section of this protocol ([Section 8.14.1](#))

Under these circumstances, the investigator's SAE awareness date is the date that the investigator receives the nonendpoint SAE back from the EAC.

All other events that meet SAE criteria will be reported by the investigator as described in previous sections.

Figure 2. Protocol-Specified SAE Reporting

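### Protocol 7.1.1 reports a BSI or SSI only if the investigator finds the clinical criteria met, while 8.6.1 sends every suspected one to the event adjudication committee

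*Protocol*

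**What the plan says.** The protocol gives two triggers for reporting a possible primary-endpoint infection.

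**Suspicion**
- Section 8.6.1: "Any suspected BSI or SSI event has the potential to meet endpoint criteria and is therefore to be adjudicated by the EAC". This is the only one of the passages compared here that names the EAC for suspected events.
- Section 6.4.2: at any point after surgery, "when a subject is suspected of having a BSI and/or SSI, a BSI/SSI assessment visit will be conducted". The first procedure listed for that visit is a PDI event report, with a pointer back to 7.1.1. If the visit cannot be done, for instance because outside staff have already treated the infection, "a PDI event report will be completed regardless".

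**Investigator-confirmed criteria**
- Section 7.1.1: the investigator first reviews each suspected PDI against Appendix 1. "Where the clinical criteria are met, the following procedures will be conducted": notify the sponsor, complete the 6.4.2 (or ISA) requirements, and report the event in the CRF.
- Section 7.1.1, for infections managed by an outside physician or hospital: "If the clinical criteria are met, the investigator will complete the PDI event report noted above and notify the sponsor".

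**Who decides on the criteria.** Section 2.5: "The EAC is responsible for adjudicating whether BSI and SSI events fulfill the protocol-defined clinical criteria". The same section limits the EAC's workload to events that have been reported. SAP 6.1 likewise leaves the case definition to the EAC.

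**Table 4** uses suspicion as its trigger ("If a PDI event is suspected, complete PDI event requirements"), but its footnote defers to 7.1.1. It is therefore not itself in conflict.

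**The concern.** The primary endpoint is defined as EAC-confirmed. If the site must first find the same clinical criteria met, an event counts only when both the investigator and the EAC say yes, and the first of these decisions lies outside blinded central adjudication. Section 9.3 assumes perfect classification for the SSI endpoints, with no case overlooked. A site filter puts that assumption at risk.

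There is a safety side too. Section 8.6.1 exempts suspected and confirmed BSI and SSI from investigator SAE reporting, unless the investigator judges the product to be the cause. It relies on the EAC to send non-endpoint events back to the site for SAE reporting. An event that stops at the site never reaches the EAC, so nothing comes back to start that report.

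**Working it through.** **1. The texts side by side**

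| Step | 8.6.1 and 6.4.2 | 7.1.1 |
|---|---|---|
| Start of BSI/SSI visit procedures | Suspicion (6.4.2) | After criteria are met |
| PDI event report | Suspicion (6.4.2) | After criteria are met |
| Infection treated outside the study | Report even if the visit cannot be done (6.4.2) | Report only if criteria are met |
| Reaches the EAC | Any suspected event (8.6.1) | Reported events only (with 2.5) |

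The order in 7.1.1 is also circular. Both BSI criteria in Appendix 1 need a positive blood culture, and 6.4.2 is the section that calls for blood cultures when a BSI is suspected. Yet 7.1.1 places the 6.4.2 requirements after the criteria have been met.

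The cross-references do not settle the matter. The visit sections (6.3.1.2.1, 6.3.2 to 6.3.5, 6.4.3) route a suspected PDI through 7.1.1 and, if it represents a BSI or SSI, also through the assessment-visit procedures. Those procedures point back to 7.1.1 for the report.

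**2. Would a planned analysis recover a screened-out event?** SAP section 7 reassigns only suspected PDIs that meet the clinical criteria but lack microbiology. The follow-up-time analysis in SAP 8.1.1 changes only the denominator. Neither reaches an event stopped at 7.1.1.

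**3. The plan's own figures.** Inputs from protocol 9.1 and 9.2: 48 cases, placebo incidence 1.4%, dropout 10%, 1:1 allocation.

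N = 48 / [(1 − 0.10) × 0.5 × 0.014 × (2 − VE)]

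- VE 70%: 48 / 0.00819 = 5,861 (stated: about 6000).
- VE 60%: 48 / 0.00882 = 5,442 (stated: 5440).
- Power at VE 70%: exact binomial with p = (1 − VE)/(2 − VE) = 0.2308 and at most 14 of 48 gives 0.878 (stated: 0.88).

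All three reproduce. No figure in the plan is disputed.

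**4. Illustration of size.** The loss fractions f are assumptions; the documents give none.

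Equal loss in both arms, N/(1 − f) at VE 70%:

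| f | True cases needed to count 48 | Subjects | Added to 5,861 |
|---|---|---|---|
| 5% | 50.5 | 6,169 | 308 |
| 10% | 53.3 | 6,512 | 651 |
| 20% | 60.0 | 7,326 | 1,465 |

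VE stays unbiased, and power at 48 counted cases is unchanged.

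Loss in the SA4Ag arm only, true VE 20%. Apparent RR = 0.80 × (1 − f) and p = RR/(1 + RR). Rejection means at most 3 of 24 at the interim or at most 14 of 48 at the end:

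| f | Apparent VE | 1-sided rejection probability |
|---|---|---|
| 0 | 20% | 2.2% |
| 5% | 24% | 3.3% |
| 10% | 28% | 4.9% |
| 20% | 36% | 10.5% |

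Loss confined to the placebo arm would bias VE downwards.

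**The case against.** The other side has good points, and most of them narrow the finding.

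- **A suspicion-based route exists.** Section 6.4.2 starts the visit and its event report on suspicion for exactly the infections in the primary endpoint. A reader might infer that 7.1.1 is the rule sites actually follow. The documents do not show that; they show two competing instructions.
- **Only 8.6.1 names the EAC.** A reader might infer that Table 4 and 6.4.2 also send every suspected event there. They ask for the PDI requirements or report. The EAC step follows from 2.5 and 7.1.1.2, and Table 4 defers to 7.1.1.
- **The unconditional report in 6.4.2** may mean regardless of whether the visit took place, not regardless of the criteria. That reading is fair, and it softens the clash for outside-treated infections. The trigger in that paragraph is still suspicion.
- **A true case must meet Appendix 1 anyway.** It is lost only if the investigator misjudges it or lacks data. There are backstops: *S aureus* isolates go to the central laboratory (7.3.1), antibiotic use is recorded (5.4), later admissions are checked daily (6.4.3), and deaths and multiple-organ failure go to the EAC (7.2.3, 7.2.3.1). These reduce the risk. However, the isolate and antibiotic rules do not state that they trigger a PDI report, and 6.4.3 leads back to 7.1.1.
- **The SAE gap is partly covered.** Section 8.6.1 ends with a residual rule that other events meeting the seriousness criteria are reported, and 6.4.2 asks for an AE/SAE check at the visit. A reader might infer that screened-out events necessarily escape SAE reporting; the text does not support that. Figure 2 and the study reference manual, which may say more, are not available here.
- **Unequal loss is conjecture.** Investigators review e-diary reactions (7.2.1.1) and so might guess allocation. The documents give no unblinding rate and no evidence of differential reporting.
- **Enrollment has ended** (SAP 8.1.3.5), so the added subjects show a design cost, not a recruitment need.

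What remains is the contradiction itself.

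**Conclusion.** The point holds as a conflict in the current protocol text. Section 7.1.1 disagrees with 8.6.1 and 6.4.2 on whether suspicion or an investigator's finding on the criteria triggers reporting. It also places ahead of the EAC a judgement that 2.5 gives to the EAC. Followed literally, 7.1.1 can remove a misjudged or poorly documented case before blinded adjudication, with no planned analysis to recover it and only a partial net on the SAE side.

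The size cannot be derived from the documents. The 5%, 10% and 20% losses are assumptions for scale. Equal loss costs enrollment only; unequal loss biases VE and, if it falls on the SA4Ag arm, raises the false-positive rate. Nothing in the documents shows that cases were in fact lost, or that loss differed by arm.

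**What to change.** In 7.1.1, make suspicion the trigger. Every suspected BSI or SSI is reported on the PDI form and sent to the EAC, including one treated outside the study and any Table 7 infection that could be an organ/space SSI. The investigator's view on the Appendix 1 criteria is recorded but is not a condition for reporting. Change the matching sentence on outside-treated infections in the same way.

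Do not keep a site filter for Table 7 infections. Osteomyelitis, disc space infection, meningitis and spinal abscess are on that list, but they count as organ/space SSI when index-surgery tissue is involved. Section 7.1.1.2 in any case sends all PDIs to the EAC.

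In 8.6.1, state that a suspected event not sent to the EAC falls under ordinary AE/SAE reporting.

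The cost is protocol wording and some extra EAC dossiers. No added subjects, visits or procedures are needed.

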1. INTRODUCTION

Staphylococcus aureus (*S aureus*) is a gram-positive coccus and a commensal organism that colonizes the nares, axillae, pharynx, and other mucosal and skin surfaces of approximately 20% to 50% of humans.^{1,2} *S aureus* is an opportunistic pathogen² and a leading cause of healthcare-associated infections (HAIs), including bloodstream infection (BSI), surgical-site infection (SSI), and hospital-acquired pneumonia (HAP),^{2,3} and is an increasingly common cause of community-associated infections in the United States (US), Europe, and globally. Among North American, Latin American, European, and Western Pacific nations, *S aureus* is recognized as the leading cause of HAIs.⁴ In the United States, *S aureus* is estimated to represent 15% of all HAIs.⁵ In the outpatient setting, *S aureus* has been estimated to be responsible for 11.6 million skin and soft tissue infections (SSTIs) annually in the United States, affecting 411/10,000 persons.⁶ Likewise, globally *S aureus* is the predominant cause of SSTI, representing 45% of North American, 34% of Latin American, and 38% of European isolates.⁷

The widespread disease manifestations of *S aureus* and its substantial burden to the healthcare system present a serious unmet medical need. Infections due to methicillin-sensitive *S aureus* (MSSA) as well as those due to methicillin-resistant *S aureus* (MRSA) contribute to disease morbidity, mortality, and economic burden, as well as the increasing need for more rigorous infection control practices. Despite the availability of antibiotics indicated for the prevention and treatment of *S aureus* infections, outcomes remain suboptimal for many patients.² Given the failure of the current standards of care to address the global epidemic of *S aureus* disease, the need for a preventive vaccine is clear.

1.1. Mechanism of Action/Indication

S aureus 4-antigen vaccine (SA4Ag) is intended for active immunization for the prevention of postoperative invasive disease caused by *S aureus* in adults 18 years of age and older who are undergoing elective surgery.

1.2. Background and Rationale

1.2.1. Healthcare-Associated *S aureus* Disease

S aureus is among the most prevalent pathogens responsible for HAIs in numerous healthcare settings. Based on data from the Nationwide Inpatient Sample (NIS), from 2000 to 2001 approximately 0.8% of all US hospitalizations involved *S aureus* infections,⁸ and in 2001, 1.1% of US surgical hospitalizations⁹ involved *S aureus* infections. Inpatients with *S aureus* infection have an estimated 3 times the length of hospital stay and 5 times the risk of in-hospital death as patients without *S aureus* infection.⁸ The risk of developing *S aureus* infection is dependent on factors related to both the patient and the type of healthcare exposure. At-risk populations include patients undergoing surgery, patients with end-stage renal disease, patients in intensive care units (ICUs), transplant recipients, and other immunocompromised individuals.^{10,11,12} Medically or surgically managed conditions associated with increased exposure to the healthcare system place individuals at further risk of acquiring healthcare-associated *S aureus* infection.^{13,14}

S aureus has been demonstrated to be the leading cause of BSI, responsible for 20% to 26% of infections overall among North American, European, and Latin American countries,¹⁵ and for 19% of infections among developing countries globally.¹⁶ A large international study recently estimated the population incidence of *S aureus* BSI to be 26.1/100,000 among several developed nations.¹⁷ *S aureus* is the leading cause of both hospital-acquired (34%) and ventilator-associated (27%) pneumonia,¹⁸ and is commonly identified as the predominant organism isolated among intensive care patients^{12,19} and hospitalized pediatric patients.²⁰

